1 INTRODUCTION

This document is the clinical investigation plan (CIP) for the Advisor HD Grid Observational Study. This clinical study is a prospective, multi-center, observational study intended to quantify and characterize the outcomes of radiofrequency (RF) ablation after, and the utility of electroanatomical mapping with the market-released Advisor™ HD Grid Mapping Catheter, Sensor Enabled™ in subjects with persistent atrial fibrillation (PersAF) or ventricular tachycardia (VT) in the real-world environment. This clinical study is sponsored by Abbott.

This clinical study will be conducted in accordance with this CIP. All investigators involved in the conduct of the clinical investigation will be qualified by education, training, or experience to perform their tasks and this training will be documented appropriately.

1.1 Background and Rationale

1.1.1 Background

Atrial Fibrillation (AF) is a supraventricular arrhythmia characterized by rapid and irregular activation in the atria, and, when maintained greater than seven days, is known as Persistent AF (PersAF).¹ Patients with PersAF have an increased risk of stroke and are likely to develop life-threatening problems such as tachycardia-induced cardiomyopathy and congestive heart failure which can increase mortality. Restoration and maintenance of sinus rhythm in these patients may confer mortality benefit.^{1,2}

Sustained monomorphic VT is a cardiac arrhythmia emanating from the ventricles at a rate greater than 100 bpm that is sustained longer than 30s or requires intervention due to hemodynamic instability.³ Sustained VT is associated with increased mortality risk including risk of sudden cardiac death. Patients are often implanted with an implantable cardiac defibrillator (ICD) for treatment when episodes occur, although treatment with an ICD is not curative and is associated with increased mortality and decreased quality of life. Treatment to avoid recurrent symptoms is therefore both desirable and may improve survival in patients.⁴

Catheter ablation is an established treatment option for PersAF and VT, although corresponding success rates in long-term sinus rhythm maintenance remain modest and could benefit from further research. Ablation strategies target the pathogenic mechanisms that initiate and perpetuate abnormal electrical activity within the heart including abnormal substrate. However, identifying and eliminating the pathogenic mechanisms is not straightforward, especially with complex arrhythmias such as PersAF and VT in which the distribution of potential arrhythmogenic drivers is heterogeneous across the patient population and there remains a lack of consensus on approach to identifying and ablating mechanistic drivers.

PersAF is electrophysiologically characterized by fast and regular atrial activities, complex fractionated atrial electrograms, direction of wave front propagation, and low peak-to-peak voltage. Potential drivers of PersAF beyond pulmonary vein triggers may include areas of fibrosis, focal automaticity, or foci, areas of rapidly rotating reentrant circuits, or rotors, asynchronous activation of myocyte bundles identified by complex fractionated electrograms, overactive ganglionated plexi, and dissociation and interaction between epicardial and endocardial layers.^{1,5,6} The role of such mechanisms continues to be debated along with their implication on therapeutic strategy, especially since ablation techniques aim to eliminate AF triggers or modify arrhythmogenic substrate. Similarly, the majority of patients with sustained monomorphic VT requiring therapy have some type of structural heart disease, and VT associated with

Clinical Investigation Plan

structural heart disease is characterized by scar tissue and slow conduction zones which form a critical isthmus.⁴ Multiple techniques are used to both locate such pathologic substrate including identification of local abnormal ventricular activities (LAVA), late potentials, fractionated electrogram signals, and wavefront mapping, and to guide ablation strategies including targeting all LAVA or late potentials, scar homogenization, and dechanneling.⁷

Recent advancements in high-density three-dimensional catheter mapping strategies enable the evaluation of such electrophysiologic characteristics that are used as surrogates for identifying the mechanisms responsible for PersAF and VT.^{6,7} Identification of electrophysiological characteristics depends on the ability of mapping catheter electrodes and electrode pair electrograms to detect voltage characteristics. However, unipolar and/or bipolar EGM amplitudes may be influenced by the direction of the wavefront, catheter orientation, electrode size, interelectrode spacing, proximity to tissue and contamination by far-field signals.⁷ Accurate electrogram depiction of underlying substrate is limited by adequate bipole orientation which can be challenging to achieve with traditional linear mapping catheters, noncompliant catheters unable to make adequate tissue contact, and high density mapping catheters with inconsistent electrode spacing. The Advisor™ HD Grid, Sensor Enabled™ (HD Grid) diagnostic mapping catheter with equispaced multipolar grid electrodes provides known bipole spacing in orthogonal directions, thereby providing the ability to discriminate voltage differences in two directions for enhanced directionality and amplitude detection. This is done by using the HD Wave electrode configuration with AutoMap best duplicate enabled during electroanatomical map creation (Appendix V). It is hypothesized that the use of HD Wave mapping will allow high-resolution substrate identification, but the impact of this mapping catheter and configuration on the subsequent ablation strategy used by physicians remains unknown.

1.1.2 Rationale for Conducting this Clinical Study

The HD Grid catheter is a recently launched multielectrode catheter with electrodes evenly distributed in a grid to allow for orthogonal bipole orientations that may overcome current multielectrode catheter limitations. Not much is known about how HD Grid is used clinically in the real world, with published literature including only two case reports.^{8,9} It is hypothesized that electroanatomical mapping with the HD Grid catheter and HD Wave mapping will provide high-density and high-resolution mapping for improved insight to the extent of structural disease and assist in the determination of the “critical” atrial/ventricular targets to guide catheter ablation strategy. This can allow physicians to avoid both unnecessary overtreatment that could result in increased risk of complication, procedure duration, and fluoroscopy exposure, and undertreatment with increased likelihood of recurrence in patients that present with complex arrhythmias.

Therefore, investigation of the new-to-market HD Grid mapping catheter will be useful in elucidating how the high-density, multielectrode catheter and HD Wave mapping configuration are used to identify arrhythmogenic heterogeneous substrate in complex PersAF and VT substrate, guide ablation strategy, and achieve favorable procedural characteristics, while overcoming current limitations to traditional multielectrode catheters.

2 CLINICAL STUDY OVERVIEW

2.1 Clinical Study Objective

The aim of this study is to quantify and characterize the outcomes of radiofrequency (RF) ablation after, and the utility of electroanatomical mapping with the Advisor™ HD Grid Mapping Catheter, Sensor

Clinical Investigation Plan

Enabled™ (hereafter called “HD Grid”) and EnSite Precision™ Cardiac Mapping System (SV 2.2 or higher, hereafter called “EnSite Precision”) with HD Wave Vmax voltage mapping (hereafter called “HD Wave”) in subjects with PersAF or VT in real-world clinical settings. This will be completed through the assessment of two main objectives which are as follows:

2.1.1 Outcomes Objective:

The first objective is to quantify and characterize the acute- and long-term success rate of RF ablation after electroanatomical mapping with HD Grid and EnSite Precision with HD Wave in subjects with PersAF or VT.

2.1.2 Utility Objective:

The second objective is to quantify and characterize the use of HD Grid and EnSite Precision with HD Wave in the electroanatomical mapping of PersAF or VT in real-world clinical settings.

2.2 Device(s) To Be Used in the Clinical Study

2.2.1 Names of Devices Used in the Study

All devices used in this clinical study must have proper regulatory approval and will be used according to their indications for use and Instructions for Use (IFU).

The devices that will be used in this clinical study are summarized in Table 1.

Table 1. Clinical Study Devices

Device name	Model/Type	Manufacturer
Advisor™ HD Grid Mapping Catheter, Sensor Enabled™	D-AVHD-DF16	SJM
EnSite Precision™ Cardiac Mapping System v 2.2 or later	H702496	SJM
Advisor™ HD Grid Mapping Catheter, Sensor Enabled™ Software Kit (License entitlement to use HD Grid Catheter with EnSite Precision 2.2)	H702519	SJM
Sensor Enabled™ Diagnostic Catheter Cable	D-AVSE-CBL22	SJM
EnSite Precision™ Surface Electrode Kit	EN0020-P	SJM
EnSite™ AutoMap Module	H702498	SJM

Clinical Investigation Plan

Additional commercially available tools may be used in this clinical study, per physician's discretion and per device IFUs.

2.2.2 Intended Indication for Use

Indications for use may be found in the appropriate device IFU. Indications for the use of HD Grid and EnSite Precision are described below.

The Advisor™ HD Grid Mapping Catheter, Sensor Enabled™, is indicated for multiple electrode electrophysiological mapping of cardiac structures in the heart, i.e., recording or stimulation only. This catheter is intended to obtain electrograms in the atrial and ventricular regions of the heart.

The EnSite Precision™ Cardiac Mapping System is a catheter navigation and mapping system capable of displaying the three-dimensional (3D) position of conventional and sensor enabled electrophysiology catheters, as well as displaying cardiac electrical activity as waveform traces and as dynamic 3-D isopotential maps of the cardiac chamber. The contoured surfaces of these three-dimensional maps are based on the anatomy of the patient's own cardiac chamber.

The EnSite Precision™ Cardiac Mapping System (including AutoMap) is a suggested diagnostic tool in patients for whom electrophysiology studies have been indicated.

The EnSite Precision™ system interfaces to either MediGuide™ Guided Medical Positioning System or the EnSite Precision™ Module to combine and display magnetic processed patient positioning and orientation mapping information. When used with an EnSite Precision™ Surface Electrode Kit, the EnSite Precision™ Cardiac Mapping System is intended to display the position of conventional electrophysiology (EP) catheters in the heart.

2.2.3 Description of the Devices Used in this Study

Please refer to the IFU for additional information regarding the devices used in this clinical study.

3 CLINICAL STUDY DESIGN

This is a prospective, non-randomized, multicenter observational study to quantify and characterize the outcomes of RF ablation after, and the utility of electroanatomical mapping with HD Grid and the EnSite Precision with HD Wave in subjects with PersAF or VT in real-world clinical settings. A total of 500 subjects will be enrolled at up to 30 investigational sites worldwide.

Subjects will be followed for up to 12-months after their initial ablation procedure. The outcome and utility descriptive endpoints will be evaluated when all subjects have completed their long-term follow-up visits (12-months for PersAF and 6-months for VT). Additional descriptive endpoints will be evaluated when all subjects have completed their 12-month follow-up visits.

[figure not shown]
3.1 Clinical Study Procedures and Follow-up Schedule

Subjects will be consented for the trial prior to any data collection. Once eligibility is confirmed and a subject is consented, baseline information will be collected and the subject will undergo the RF ablation procedure per physician discretion using electroanatomical mapping with the HD Grid mapping catheter. Subjects will be followed for 12-months post procedure. Follow-up assessments will occur either in person at a clinic or via phone contact after the procedure. The study visits will occur at baseline,

Clinical Investigation Plan

procedure, pre-discharge, and 6- and 12-months post ablation procedure. The subject will be exited from the study after completion of the 12-month follow-up visit. The visit schedule and related study assessments are summarized in Figure 1, and further detail provided in section 6.

Figure 1. Clinical Study Flow Chart

Clinical Investigation Plan

3.2 Measures Taken to Avoid and Minimize Bias

Multiple measures will be taken to avoid bias in this clinical study. First, the Advisor HD Grid Observational Study is prospective, such that the outcome of the study is unknown at time of enrollment, and all subjects must meet pre-defined eligibility criteria thereby minimizing selection bias. Next, guidance will be provided to sites regarding data collection for questionnaires and post-procedure follow-up visits and/or phone calls, and case report forms for data collection will be provided to all sites thereby minimizing inter-observer variability. Evaluation of arrhythmia recurrence via Holter monitoring will be performed by an independent core laboratory. Adverse events will be internally assessed by the Sponsor independent of assessment by the physician as reported by the site. Additionally, protocols are in place to minimize subjects lost to follow-up and collection of missing data to minimize the impact or bias caused by missing data.

3.3 Suspension or Early Termination of the Clinical Study

No formal statistical rule for early termination of the clinical study is defined.

The Sponsor reserves the right to discontinue the clinical study at any stage or reduce the follow-up period or sample size with suitable written notice to the investigator.

Should the clinical study be discontinued by the Sponsor, subjects will be followed per routine hospital practice with device-related AEs reported to the Sponsor as per vigilance/commercial reporting requirements.

Should this occur, the investigator shall provide a written statement as to why the premature termination has taken place to the IRB/EC (if applicable). All applicable clinical study documents shall be subject to the same retention policy as detailed in Section 11 of the CIP.

A Principal Investigator, IRB/EC, or regulatory authority may suspend or prematurely terminate participation in the clinical study at the investigational sites for which they are responsible. The investigators will follow the requirements specified in the Clinical Trial Agreement.

If the Sponsor suspends or prematurely terminates the clinical study at an individual site in the interest of safety, the Sponsor will inform all other Principal Investigators.

4 ENDPOINTS

The objectives of this study will be addressed through multiple descriptive endpoints and will be reported using summary statistics. All descriptive endpoints will be evaluated independently for the PersAF and VT subjects.

4.1 Descriptive Endpoint(s)

4.1.1 Outcomes Objective

The first objective is to quantify and characterize the acute- and long-term success rate of RF ablation after electroanatomical mapping with HD Grid and EnSite Precision with HD Wave in subjects with PersAF or VT.

Clinical Investigation Plan

To quantify and characterize the acute- and long-term success rate of RF ablation after electroanatomical mapping with HD Grid, the following will be summarized:

- Rate of acute success defined as the proportion of subjects who receive HD Grid mapping and RF energy delivery resulting in acute termination of clinical arrhythmia, defined by termination to SR (or AT if being treated for PersAF) or non-inducibility of clinical arrhythmia after ablation (cardioversion allowed prior to inducibility attempt).
- Rate of long-term success defined as the proportion of subjects who receive HD Grid mapping and RF energy delivery with the following pre-defined procedural endpoints:
 - Persistent AF (utilizing a 90-day blanking period following index ablation):
 - freedom from all atrial arrhythmias (AF/AFL/AT) greater than 30 seconds (as documented by 48-hr Holter at 12-month follow-up) and new or increased dose of class I/III antiarrhythmic drug (AAD).
 - freedom from all atrial arrhythmias (AF/AFL/AT) greater than 30 seconds (as documented by 48-hr Holter at 12-month follow-up) on or off class I/III AAD.
 - VT (utilizing a 14-day blanking period following index procedure):
 - freedom from recurrence of sustained monomorphic VT and new or increased dose of class I/III AAD at 6-month follow-up
 - freedom from recurrence of sustained monomorphic VT on or off class I/III AAD at 6-month follow-up.

Where recurrence of sustained monomorphic VT is defined as:

- Sustained monomorphic VT greater than 30s or requiring appropriate ICD pacing or shocks for patient with ICDs
- Sustained monomorphic VT greater than 30s recorded in follow-up visits or requiring intervention due to hemodynamic instability for patients without ICDs

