5.3.3 Exclusion Criteria

1. Life expectancy less than 12 months

Clinical Investigation Plan

2. Women who are pregnant or nursing
3. Known intracardiac thrombus or myxoma verified within 48 hours of index ablation procedure
4. Myocardial infarction (MI) or unstable angina, or previous cardiac surgery within 60 days of index ablation procedure
5. Percutaneous coronary intervention (PCI) within 30 days of index ablation procedure
6. Documented cerebroembolic event within the past 12 months (365 days)
7. History of valve repair, presence of a prosthetic valve, or severe mitral regurgitation thought to require valve replacement or repair within 12 months
8. Awaiting cardiac transplantation or other cardiac surgery within the next 12 months (365 days)
9. Current acute illness or active systemic infection or sepsis
10. Currently enrolled in another clinical study that could confound the results of this study
11. Any cause for contraindication to ablation procedure or systemic anticoagulation
12. Presence of other anatomic or comorbid conditions, or other medical, social, or psychological conditions that, in the investigator's opinion, could limit the subject's ability to participate in the clinical study or to comply with follow-up requirements, or impact the scientific soundness of the clinical study results.
13. Vulnerable patient or individuals whose willingness to volunteer in a study, in the judgement of investigator or public authorities, could be unduly influenced by lack of or loss of autonomy
14. Indication-specific exclusion criteria including:
 - a. PersAF:
 - i. PersAF felt to be secondary to electrolyte imbalance, uncontrolled thyroid disease, or reversible or non-cardiac cause.
 - ii. LAD > 55 mm (parasternal long axis view)
 - iii. LVEF < 40%
 - iv. Uncontrolled heart failure or NYHA function class III or IV
 - v. Presence of implanted ICD/CRT-D.
 - b. VT:
 - i. VT/VF thought to be from channelopathies
 - ii. Active ischemia or other reversible cause of VT
 - iii. Incessant VT at time of procedure
 - iv. Implanted with a ventricular assist device (VAD) (e.g. TandemHeart)
 - v. Chronic NYHA Class IV heart failure
 - vi. Ejection fraction < 15%

Incessant VT is defined as continuous sustained VT that promptly recurs despite repeated intervention for termination over ≥ 3 hours.

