6.2 Procedure Visit

The procedure should be performed according to the IFU of the HD Grid mapping catheter, EnSite Precision™ Cardiac Mapping System, and any other medical devices used during the procedure. Physicians performing electroanatomical mapping and ablations must be qualified operators and trained on the study. Each physician who ablates during a particular case needs to be documented on the Procedure CRF.

The following information will be collected during the Procedure Visit:

- Antiarrhythmic medications- any current class I/III AAD and dose
- Anticoagulant medications
- Subject cardiac rhythm when they enter the EP lab
- Subject cardiac rhythm during mapping
- Mapping and ablation tools used during the procedure
- Procedural characteristics (set up and timing)
- Fluoroscopy time
- Mapping time (total time to collect mapping data and time for each map created/ retrospectively generated)
- Mapping points collected and used for each map created/ retrospectively generated
- Mapping location(s)
- Electrode configuration used for clinical electroanatomical mapping
- Map type(s) (i.e. Voltage, LAT, CFE, etc.)
- AutoMap settings used (if applicable)
- Arrhythmogenic substrate identified
- Field Scaling use
- Standard and HD Wave map comparisons
- Ablation strategy
- AutoMark settings used (if applicable)
- Cardioversions performed during procedure
- Attempt(s) at induction of arrhythmia as applicable before and after RF delivery
- Subject rhythm after completion of procedure

The entire case (procedure) must be recorded and stored on a study-specific USB (password-protected), provided by the Sponsor, and returned within a reasonable timeline to the Sponsor.

Protocol deviations (refer to Section 10.5 for details) that were observed during the procedure, which include any device used off-label during the procedure, will also be recorded at this time.

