Create a baseline geometry and map (at a minimum, collect baseline voltage map, other maps may be collected per standard of care) of the ventricle(s) using HD Grid with HD Wave electrode configuration. Create or retrospectively generate any additional electroanatomical maps (may include generation of maps with along-the-spline configuration, preferably using TurboMap with same geometry; see Appendix V). Use the voltage HD Wave map, and/or other maps as clinically necessary to identify ablation target(s). Use ablation catheter per IFU to perform ablation per standard of care. Attempt to re-induce any VT ablated if possible. Assess acute procedural success. Create post-ablation voltage map or collect additional maps and perform additional ablation if clinically necessary.

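### The termination limb of acute success credits VT subjects only for return to sinus rhythm, so a VT stopped by RF into AF or a paced rhythm counts only if non-inducibility is also shown

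*Combined protocol and SAP*

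**What the plan says.** Acute success is the first outcome listed under the first objective (section 4.1.1). Its numerator and denominator are set by "the proportion of subjects who receive HD Grid mapping and RF energy delivery resulting in acute termination of clinical arrhythmia". That phrase is then given an operational definition with two limbs: "defined by termination to SR (or AT if being treated for PersAF) or non-inducibility of clinical arrhythmia after ablation". The second limb continues with an allowance for cardioversion: "or non-inducibility of clinical arrhythmia after ablation (cardioversion allowed prior to inducibility attempt". Section 4 says that endpoints are evaluated independently for PersAF and VT, but no separate VT termination limb is written.

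In section 5.3.3, item 14a excludes PersAF subjects for "Presence of implanted ICD/CRT-D". The VT list, item 14b, has no such entry and does not mention underlying AF or paced rhythm. VT subjects with ICDs are expected: section 4.1.1 defines VT recurrence for them, and Table 2 schedules ICD interrogation for VT only.

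For the VT procedure, section 6.2.3.2 says "Attempt to re-induce any VT ablated if possible. Assess acute procedural success". Section 6.2 collects "Attempt(s) at induction of arrhythmia as applicable before and after RF delivery", rhythm on entering the EP lab and during mapping, cardioversions, and "Subject rhythm after completion of procedure". It also requires the whole case to be recorded and returned to the sponsor.

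**The concern.** For VT, the arrhythmia being treated is ventricular. When RF ends it, the subject goes back to whatever the underlying rhythm is, which may be sinus, AF or paced. The termination limb recognises only the first of these. Because an alternative rhythm is spelled out for PersAF alone, it is hard to read SR loosely for VT.

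Two VT subjects with the same response to RF can therefore be scored differently because of atrial rhythm or pacing status, which the VT ablation is not treating. The reported VT rate would then depend partly on how many AF and paced subjects happen to be enrolled. Sites or programmers could also score the same case differently, some by the general idea of ending the clinical arrhythmia and some by the literal SR wording.

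**Working it through.** The plan states no expected acute success rate, power or margin for this endpoint, so there is no figure to reproduce. The check has two parts.

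**1. The rule applied to VT subjects in whom RF stops the clinical VT** (section 4.1.1, limbs joined by *or*):

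| Re-induction after RF | Returns to sinus rhythm | Returns to AF or paced rhythm |
|---|---|---|
| Done, not inducible | credited (both limbs) | credited (second limb) |
| Not done | credited (first limb) | not credited |
| Done, still inducible | credited (first limb) | not credited |

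The columns differ in the last two rows. The *not done* row can occur because section 6.2.3.2 qualifies the request, "Attempt to re-induce any VT ablated if possible", and section 6.2 records induction only as applicable. The available text has no scoring rule for untested subjects, and section 8.7 says missing data are not imputed.

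**2. Size.** Let
- a = share of VT subjects whose underlying rhythm is AF or paced,
- t = share of those in whom RF stops the VT,
- u = share of those not shown non-inducible (untested or still inducible).

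Each share is conditional on the one before, so the product needs no independence assumption:

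understatement (percentage points) = 100 × a × t × u

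Uncredited subjects are kept in the denominator, which in 4.1.1 is everyone with HD Grid mapping and RF delivery. The documents give none of a, t or u; all values below are assumptions.

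- u = 0 (all such subjects tested and non-inducible): 0 points for any a and t.
- a = 0.10, t = 0.40, u = 0.1: 100 × 0.10 × 0.40 × 0.1 = 0.4 points.
- a = 0.10, t = 0.40, u = 0.3: 1.2 points.
- a = 0.10, t = 0.40, u = 0.5: 2.0 points.
- Low corner, a = 0.05, t = 0.20, u = 0.1: 0.1 points.
- High corner, a = 0.30, t = 0.60, u = 0.5: 9.0 points.

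Section 3 gives 500 subjects for both cohorts together. The available text gives no VT number, so the points cannot be turned into a subject count for this study.

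**The case against.** A reader might infer from the termination wording that VT subjects must reach sinus rhythm, so that one in AF or paced rhythm can never be an acute success. The documents do not support that. Non-inducibility is a full alternative, carries no rhythm condition and is open to every VT subject. It is also the planned route for VT: re-induction comes immediately before acute success is assessed, incessant VT at the time of procedure is excluded (item 14b), and section 5.1 describes substrate-based VT. Treating the second limb as absent (u = 1) would give 1.0 to 18.0 points over the same a and t, but nothing in the text justifies u = 1.

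Three further objections have weight. First, absence of an ICD exclusion does not show that a subject is paced or out of sinus rhythm; it shows only that such subjects can be enrolled. Second, the same *or* is lenient elsewhere, since a VT that terminates to SR but stays inducible is a success. The understatement is therefore relative to a rule that credits RF termination whatever the underlying rhythm, and is not a statement about the overall strictness of the endpoint. Third, the endpoint has no hypothesis test (section 8.2.2) and no pass/fail criterion (section 8.10).

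These points limit the size and consequence. They do not remove the last two rows of the table, where underlying rhythm alone decides the score.

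**Conclusion.** The gap is real and narrow. Under the literal text, a VT subject whose clinical VT is stopped by RF into AF or a paced rhythm, and who is untested or still inducible, is not credited; the same subject returning to sinus rhythm is. On this point the wording can only lower the VT acute success rate or leave it unchanged.

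That the rate *is* understated cannot be concluded, because the effect is 0 if all such subjects are tested and non-inducible. Under the illustrative shares it is 0.4 to 2.0 points. The 9.0-point upper end needs all three assumed shares at their maximum together. The point is worth correcting because it misclassifies a foreseeable subset in a main outcome and is cheap to close, not because any decision turns on it.

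**What to change.** In section 4.1.1, write the termination limb separately by cohort. For VT: *termination of the clinical VT during RF delivery to the subject's underlying non-VT rhythm (sinus, atrial fibrillation/flutter or paced)*. Keep SR or AT for PersAF only, and leave the non-inducibility limb as it is.

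State that the VT limb is scored from the recorded case together with the section 6.2 data on rhythm, cardioversions and induction attempts. End-of-procedure rhythm alone is not enough: a VT ended by cardioversion also leaves a non-VT final rhythm, and scoring from that field would credit RF with terminations it did not produce.

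The cost is one sentence, the matching programming rule and a small amount of extra review of case recordings. No additional subjects and no change to the procedure are needed. The section 6.2 list has no explicit item for how the VT ended, and the CRFs are held under separate cover, so the sponsor should check whether the forms already capture it or whether the recordings must supply it.
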